#### **4.5.5. Physical Examination Variables**

The physical examination variable values are dichotomized to normal and abnormal.

A thorough and complete physical examination will be performed at time points according to the schedule in [Appendix 10.2](#).

#### **4.5.6. Pharmacokinetic (PK) Variables**

Samples for drug concentration will be collected at scheduled time points indicated in [Appendix 10.2 Schedule of Events](#). Due to the sparse nature of the data, only descriptive analyses will be performed. Pharmacokinetic variables may include but not limited to  $C_{trough}$  over time,  $C_{last}$  and  $T_{last}$ .

#### **4.6. Antibody (ADA) Variable**

ADA samples collected at day 1 (baseline) , Week 12 (EOT), Week 28 (EOS) and at early termination (ET) will be analyzed for ADA.

The variables include ADA response status and titer as follows:

- Total subjects negative in the ADA assay at all time points analyzed
- Total subjects with pre-existing immunoreactivity - defined as either an ADA positive response in the assay at baseline, with all post first dose ADA results negative, OR a positive response at baseline with all post first dose ADA results less than 4-fold over baseline titer levels.
- Total subjects with treatment-emergent response, defined as a positive response in the ADA assay post first dose when baseline results are negative or missing.

The treatment emergent responses will be further characterized as Persistent, Indeterminate or Transient

- Persistent Response – defined as a treatment emergent ADA response with two or more consecutive ADA positive sampling time points separated by greater than ( $>$ ) 12-week period, with no ADA negative samples or any missing sample in between.
- Indeterminate Response – defined as a treatment-emergent response with only the last collected sample positive in the ADA assay
- Transient Response - defined as a treatment emergent ADA positive assay response that is not considered persistent or indeterminate.
- Total subjects with treatment-boosted response, defined as a positive response in the ADA assay post first dose that is greater than or equal to 4-fold over baseline titer levels, when baseline results are positive
- Titer Values (Titer value category)
  - Low (titer  $<1,000$ )
  - Moderate ( $1,000 \leq \text{titer} \leq 10,000$ )
  - High (titer  $>10,000$ )

ADA positive samples will be further characterized for presence of neutralizing antibody response in the NAb assay.

## **5. STATISTICAL METHODS**

For continuous variables, descriptive statistics will include the following: the number of subjects reflected in the calculation (n), mean, median, standard deviation, Q1 and Q3, minimum, and maximum.

For categorical or ordinal data, frequencies and percentages will be displayed for each category.

### **5.1. Demographics and Baseline Characteristics**

Demographics and Baseline Characteristics will be summarized by treatment groups based on FAS. Listing of demographics and baseline characteristics will be presented.

### **5.2. Medical and EoE History**

Medical history will be summarized by primary SOC and PT for each treatment group. The table will be sorted by decreasing frequency of SOC followed by PT based on the overall incidence across treatment groups.

Medical history will be listed, sorted by treatment groups based on the SAF.

### **5.3. Pre-treatment/Concomitant Medications/Procedures**

Number and proportion of subjects taking prior/concomitant medications, prohibited medications/procedures and rescue medications/procedures will be summarized, sorted by decreasing frequency of ATC Level 2 and ATC level 4, based on the overall incidence for the dupilumab treatment group.

The procedure will be summarized by treatment group to MedDRA version 19.1 by system organ class (SOC) and preferred term (PT) and sorted by decreasing frequency of SOC and PT, based on the overall incidence for dupilumab treatment group.

Listing of pre-treatment medication and concomitant medications will include generic name and ATC levels 2 and 4, indication, study day onset (for medications started before treatment, the study day onset (defined as date of medication start - date of the first dose; for medications started on or after treatment, the study day onset = date of medication start - date of the first dose +1), the study end date (defined similarly as for study day onset), ongoing status, dose, frequency, route.

The detailed information of rescue medications/procedures including duration of use and incidence of use will be summarized. Kaplan Meier curves for time to first rescue use may be generated.

### **5.4. Subject Disposition**

The following summaries by table will be provided:

- The total number of screened patients
- The total number of randomized patients: received a randomization number
- The total number of patients in each analysis set

- The total number of patients who discontinued the study treatment and the reasons for the discontinuation
- The total number of patients who discontinued the study, and the reasons for discontinuation
- Number of patients who entered into follow-up period.

The following listings will be provided:

- Listing of subject disposition including: date of randomization, date of the last visit, received dose, completed study drug or discontinued by reason, completed study or discontinued by reason
- A listing of patients treated but not randomized, patients randomized but not treated, and patients randomized but not treated as randomized.
- A listing of patients prematurely discontinued from the study or treatment, along with reasons for discontinuation, summary tables of reasons will be provided
- Summary table with listing of protocol deviations will be provided

## **5.5. Dose administration**

The compliance with protocol-defined study drug will be calculated as follows:

Treatment Compliance =

(Number of investigational product injections]/(Number of planned investigational product injections]) x 100%

Loading doses for the same patient will be counted as 1 study drug administration.

Summary of study drug administration will include the number of study drug doses administered and treatment compliance. The treatment compliance will be presented by the following specific ranges for each treatment group for the double blind period: <80% and  $\geq$ 80%.

Listing of dose administration: including date/time, study day, number of injections, locations of injections, dosing information and whether or not the total dose is administered for each dose will be presented.

If subjects received treatment different from the randomized treatment or stopped treatment due to an AE, or overdosed, the listings will be provided.

## **5.6. Treatment Exposure and Observation Period**

The duration of treatment during the study, in days, will be presented by treatment group and calculated as:

(Date of last study drug injection– date of first study drug injection) + 7

Note: exposure will be calculated based on the last study drug injection date and first study drug injection date, regardless of temporary dosing interruption.

The duration of exposure during the study will be summarized for each treatment group using number of patients, means, SD, minimums, Q1, medians, Q3, and maximums.

In addition, the duration of exposure will be summarized categorically by counts and percentages for each of the following categories and cumulatively by these categories as well:

$\geq 7$  days,  $\geq 14$  days,  $\geq 21$  days,  $\geq 28$  days,  $\geq 35$  days,  $\geq 42$  days,  $\geq 49$  days,  $\geq 56$  days,  $\geq 63$  days,  $\geq 70$  days,  $\geq 77$  days,  $\geq 84$  days.

The duration of observation period during the study, in days, is calculated as:

[Date of the last visit of double blind and follow up period – date of the first study injection] +1.

The duration of observation period will be summarized descriptively as a quantitative data (n, mean, SD, median, Q1 and Q3, minimum and maximum). In addition, the number (%) of subjects with observation periods will be presented by specific time periods. The time periods of interest is specified as:  $\geq 8$  days,  $\geq 15$  days,  $\geq 22$  days,  $\geq 29$  days,  $\geq 36$  days,  $\geq 43$  days,  $\geq 50$  days,  $\geq 57$  days,  $\geq 64$  days,  $\geq 71$  days,  $\geq 78$  days,  $\geq 85$  days,  $\geq 113$  days,  $\geq 141$  days,  $\geq 169$  days,  $\geq 197$  days.

## 5.7. Analyses of Efficacy Variables

### 5.7.1. Hypothesis Testing and Multiplicity Control

For all efficacy variables, the analysis will be a comparison of dupilumab and the placebo treatment groups. The following null and alternative hypotheses for the primary endpoint will be tested for dupilumab group and the placebo group:

Let  $\mu_0$  and  $\mu_1$  be the population mean of the primary endpoint at week 10 under placebo and dupilumab, respectively. The hypothesis that will be tested is “ $H_0: \mu_0 = \mu_1$ ” versus “ $H_1: \mu_0 \neq \mu_1$ ”.

To account for the impact of rescue medication on the efficacy effect during 12 week double blinded period:

- Continuous efficacy endpoints: if a patient receives rescue medication, the data collected after rescue medication initiated will be treated as missing.
- Categorical efficacy endpoints: responder data will be counted as non-responders after use of rescue medication or procedure.

The analyses of efficacy variables are described in the subsections below and summarized in [Appendix 10.1](#).

There will be no adjustment of multiplicity for the secondary efficacy endpoints in this proof-of-concept study.

The efficacy data endpoints for the follow-up period will be summarized descriptively. No formal statistical test will be performed for efficacy endpoints in the follow-up period.

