Patients may receive concomitant medications (except for prohibited medications) as needed, at the discretion of the investigator, while continuing study treatment. Frequency of use and type of product will be documented. If medically necessary, rescue medications or emergency esophageal dilation may be provided to study patients. Patients receiving rescue therapy will be discontinued from study treatment. These patients will remain blinded and will be asked to return to the clinic for all remaining study treatment visits and participate in all follow-up assessments according to the visit schedule.

Efficacy, safety, and laboratory assessments will be performed at specified time points throughout the study. Samples for the assessments of dupilumab concentration and assessment of anti-drug antibody (ADA) response to dupilumab, as well as research samples will be collected at specified time points throughout the study. In response to AE's of special interest like anaphylaxis or hypersensitivity additional samples closer to the event may be collected and analyzed for ADA, based on the judgement of the medical investigator and/or medical monitor.

The end of the double-blind treatment period visit occurs at week 12, 1 week after the last dose of study drug. The maximum duration of the double-blind study is approximately 33 weeks including screening and follow-up.

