### 4.3. Pre-treatment/ Concomitant Medications and Procedures

Medications/Procedures will be recorded from the day of informed consent until the EOS visit. Medications will be coded to the ATC level 2 (therapeutic main group) and ATC level 4 (chemical/therapeutic subgroup), according to the latest available version of WHO Drug Dictionary (WHODD) version Sep 2016 at the coding of CRO. Patients will be counted once in all ATC categories linked to the medication.

Pre-treatment medications/procedures: medications taken or procedures performed prior to administration of the first study drug.

Concomitant medications/procedures: medications taken or procedures performed following the first dose of study drug through the EOS visit.

Prohibited concomitant medications/procedures during week 12 treatment period Treatment with the following concomitant medications is prohibited:

- Medications used for the treatment of EoE .
- Allergen immunotherapy.
- Patients who are not using PPI in the 8 weeks prior to screening cannot start PPI therapy prior to EOT visit
- Treatment with a live (attenuated) vaccine
- Treatment with an investigational drug (other than dupilumab)

Treatment with the following concomitant procedures is prohibited:

- Major elective surgical procedures
- Esophageal dilation (considered rescue procedure)
- Diet change.

If medically necessary (eg, for treatment of intolerable EoE symptoms) patients may be rescued with a prohibited medication or procedure at the discretion of the investigator. Patients who receive rescue treatment with a prohibited medication or procedure through week 12 will be permanently discontinued from study drug.

Rescue treatments for EoE: Blinded adjudication of rescue treatments will be implemented before database locks by considering the type of medications. A predetermined algorithm for rescue medications listed in [Appendix 10.6](#) will be used to programmatically search the concomitant medications (CMs). The rescue CMs will be reviewed and adjudicated by the medical monitor in a blinded fashion.

All patients will complete the schedule of study visits and assessments whether or not they complete study treatment. Investigators should make every attempt to conduct efficacy and safety assessments immediately before administering any rescue treatment. An unscheduled visit may be used for this purpose if necessary.

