#### 4.4.2. Secondary Efficacy Variables

The secondary endpoints are:

- Percent change in weekly Eosinophilic Esophagitis Activity Index (EEsAI) PRO score from baseline to week 10
- Change in weekly EEsAI PRO score from baseline to week 10
- Percent change in weekly EEsAI PRO score from baseline to week 12
- Change in weekly EEsAI PRO score from baseline to week 12
- Percent change in the SDI PRO score from baseline to week 10
- Percent change in the SDI PRO score from baseline to week 12
- Change in the SDI PRO score from baseline to week 12
- Change in EoE-QOL-A PRO score from baseline to week 12
- Percentage of patients with SDI PRO response at week 10; where response is defined as a decrease of at least 3 points on the SDI compared to baseline
- Percentage of patients who achieve  $\geq 40\%$  improvement in EEsAI score from baseline to week 10
- Percent change in overall peak esophageal intraepithelial eos/hpf (400X) from baseline to week 12
- Change in EoE-EREFs (endoscopy visual anatomical score) from baseline to week 12
- Percentage of patients with use of rescue medication or procedure (eg, esophageal dilation) through week 12
- Incidence of treatment-emergent AEs

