### 5.7.2. Analysis of Primary Efficacy Variables

The change in the SDI score at week 10 from baseline will be analyzed in the full analysis set (FAS) using multiple imputation (MI), with an analysis of covariance (ANCOVA) model with treatment group as fixed effect, and the baseline SDI value as continuous covariate. (primary approach).

Due to the substantial imbalance at baseline in the number of patients in the two randomization strata (only 12.8% patients in the strata of baseline SDI  $> 7$ ), the multiple imputation and ANCOVA model will not use randomization strata as a factor.

Patients' efficacy data through week 12 after rescue medication usage will be set to missing first, and then be imputed by the MI method.

Missing data from the FAS will be imputed 50 times to generate 50 complete data sets by using the SAS procedure MI following the 2 steps below:

Step 1: The monotone missing pattern is induced by Markov Chain Monte Carlo (MCMC) method in MI procedure. The monotone missing pattern means that if a patient has missing value for a variable at a visit, then the values at all subsequent visits for the same variable are all missing for the patient.

Step 2: The missing data at subsequent visits will be imputed using the regression method for the monotone pattern with adjustment for covariates including treatment groups, and baseline SDI score.

Data of each of the 50 complete datasets will be analyzed using an analysis of covariance (ANCOVA) model with treatment group as fixed effect, and the baseline SDI value as continuous covariate. SAS MIANALYZE procedure will be used to generate valid statistical inferences by combining results from these multiple analyses using Rubin's formula.

The imputation model will include:

- The covariates included in the ANCOVA model, including the treatment group and the baseline SDI value.
- Observed efficacy values from every clinic visit up to week 10

The ANCOVA model will provide least-squares means at week 10, and at other time points for each treatment group, with the corresponding standard error, confidence interval, and the p-value for treatment comparisons. The graph of LS-mean  $\pm$  SE by visit will be provided.

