#### Sensitivity analyses

In addition to the MI method described previously, sensitivity analyses for the primary efficacy endpoint will be conducted as described below:

1. The sensitivity analysis will use MI method, followed by ANCOVA based on all observed data no matter if rescue medication is used.
2. This sensitivity analysis will use ANCOVA model. The efficacy data will be set to missing after rescue medication is used. The post-baseline last-observed-case-forward (LOCF) method will then be used to impute missing values.
3. This sensitivity analysis will use ANCOVA model. The efficacy data will be set to missing after rescue medication is used. The post-baseline worst observation carried forward (WOCF) method will then be used to impute missing values.
4. This sensitivity analysis will use ANCOVA model, including all observed data, no matter if rescue medication is used.

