### **5.7.3. Analyses of Secondary Efficacy Variables**

The continuous secondary efficacy endpoints listed in Section 4.4.2 will be analyzed using the same approach as that used for the analysis of the primary endpoints. Inside step 2 of MI procedure, the missing data at subsequent visits will be imputed using the regression method for the monotone pattern with adjustment for covariates including treatment groups, baseline SDI score and relevant baseline value. Data of each of the 50 complete datasets will be analyzed using an analysis of covariance (ANCOVA) model with treatment group as fixed effect, and the baseline SDI value and relevant baseline value as continuous covariates.

Due to the substantial imbalance at baseline in the number of patients in the two randomization strata (only 12.8% patients in the strata of baseline SDI > 7), the imputation and ANCOVA will not use randomization strata as a factor. Instead the model includes the baseline SDI score as a continuous covariate.

Categorical analyses will be performed on responder data. Comparisons between dupilumab and placebo will be done using the Fisher exact test. Patients with early withdrawals or use of rescue medication or procedure will be counted as non-responders.

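### The rule that discards post-rescue values for continuous endpoints, including the primary SDI analysis, names rescue medication only, so scores after an esophageal dilation stay in the primary analysis if the text is followed

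*SAP*

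**What the plan says.** The SAP sets its post-rescue rules in several places, and their scope differs.

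**Continuous endpoints: medication only**
- Section 5.7.1: "Continuous efficacy endpoints: if a patient receives rescue medication, the data collected after rescue medication initiated will be treated as missing".
- Section 5.7.2, before the primary multiple imputation (MI): patients' "efficacy data through week 12 after rescue medication usage will be set to missing first".
- Section 5.7.2, sensitivity analyses 2 (LOCF) and 3 (WOCF): "The efficacy data will be set to missing after rescue medication is used".
- Section 5.7.3 gives the continuous secondary endpoints the same approach as the primary.

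**Categorical endpoints: medication or procedure**
- Section 5.7.1, the adjacent bullet: "responder data will be counted as non-responders after use of rescue medication or procedure".
- Section 5.7.3: "Patients with early withdrawals or use of rescue medication or procedure will be counted as non-responders".

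**Status of dilation**
- Section 4.3 lists it among procedures: "Esophageal dilation (considered rescue procedure".
- Section 4.4.2 counts it in a secondary endpoint: "Percentage of patients with use of rescue medication or procedure (eg, esophageal dilation) through week 12".
- Section 2.3 names rescue medications and emergency dilation as separate options. It says rescued patients stop study treatment but are "asked to return to the clinic for all remaining study treatment visits".

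**The concern.** Dilation is a procedure in the SAP's own classification, and no section extends the continuous rule to procedures. SDI is completed weekly through end of study or early termination (Appendix 10.2), so scores after a dilation can exist at week 10.

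One event would therefore trigger the rescue rule in the responder analysis of SDI and not in the primary analysis of the same score. If dilation changes SDI and is used unequally between arms, the primary estimate departs from what the rescue rule is meant to estimate:
- towards no difference if dilation lowers SDI and is commoner on placebo;
- away from no difference if it is commoner on dupilumab;
- unchanged if use and effect are balanced.

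The sensitivity analyses would not show this. Numbers 2 and 3 share the medication-only wording, and numbers 1 and 4 keep all observed data by design. An open rule on the primary endpoint also leaves a choice that could be made after unblinding.

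**Working it through.** **Step 1. Which reading would be programmed?** Section 4.3 identifies rescue by an algorithm that searches concomitant medications, followed by blinded adjudication of the medications found. The algorithm uses Appendix 10.6, which lists drug classes and no procedure. A rescue flag built from these sources captures no dilation. For continuous endpoints nothing else in the SAP adds it; for categorical endpoints the words *or procedure* do.

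**Step 2. One patient followed through.** Take a patient dilated at week 6, with no rescue medication and an SDI score at week 10.

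| Analysis | Handling as written |
|---|---|
| SDI response, week 10 | non-responder |
| Primary SDI change, MI + ANCOVA | week 10 score kept |
| Sensitivity 2 and 3 (LOCF, WOCF) | week 10 score kept |
| Sensitivity 1 and 4 (all observed data) | week 10 score kept, by design |

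**Step 3. Reproduce the SAP's power.** Inputs from section 2.2: 18 per arm, difference 3, SD 2.46, two-sided 5% t-test.
- Noncentrality = 3 / (2.46 × √(2/18)) = 3.66, with 34 degrees of freedom and critical value 2.032.
- Power = 94.4%, against the stated 94%.
- Enrolment: 18 / 0.85 = 21.2, rounded up to 22 per arm, as stated.

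**Step 4. Illustration of size.** The SAP gives no dilation rate or effect, so these are assumptions: *k* placebo patients dilated before week 10, none on dupilumab, each with an SDI score lower by *b* = 3 points (range 2 to 4), and SD unchanged at 2.46. With *n* per arm,

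difference = 3 − *b* × *k* / *n*.

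For example, *n* = 18 and *k* = 2 give 3 − 3 × 2/18 = 2.67.

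| *k* on placebo (*b* = 3) | Difference, *n* = 18 | Power | Difference, *n* = 22 | Power |
|---|---|---|---|---|
| 0 | 3.00 | 94.4% | 3.00 | 97.7% |
| 1 | 2.83 | 91.9% | 2.86 | 96.5% |
| 2 | 2.67 | 88.5% | 2.73 | 94.9% |
| 3 | 2.50 | 84.2% | 2.59 | 92.7% |

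For *k* = 3, moving *b* from 2 to 4 takes power from 88.5% to 78.9% at 18 per arm, and from 94.9% to 89.8% at 22 per arm.

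**Step 5. Other patterns.**
- Equal numbers dilated in both arms with the same effect, or *b* = 0: the difference stays 3.00.
- One dilation, on dupilumab only, *b* = 3: the difference rises to 3 + 3/18 = 3.17, or 3 + 3/22 = 3.14.

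**Step 6. The SD assumption.** Shifting only some placebo patients also widens the spread in that arm. Adding *b*²(*k*/*n*)(1 − *k*/*n*) to the placebo variance for *k* = 3, *b* = 3, *n* = 18 gives a placebo SD of √(6.05 + 1.25) = 2.70 and power of about 80.5% instead of 84.2%. For that case, the table understates the loss.

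**The case against.** The best defence is that rescue medication is shorthand for any rescue. The sentence introducing both bullets in 5.7.1 speaks only of rescue medication, yet one of those bullets covers procedures. Appendix 10.1 summarises sensitivity analysis 1 as being done regardless of rescue, where 5.7.2 says rescue medication. These make the shorthand reading possible. They do not make it safe: the neighbouring bullet adds *or procedure*, Appendix 10.6 defines rescue medication by drug class, and the search algorithm covers medications only. If shorthand was meant, the text still needs correcting.

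Three further points have some force.
- Continuous and responder analyses treat rescue differently by design, by imputation in one and non-response in the other. That difference is not the defect and would remain after the fix. The defect is that the triggering event differs.
- Keeping post-rescue scores is a legitimate analysis of a different question, which sensitivity analyses 1 and 4 pursue openly. The primary analysis sets out to remove the influence of rescue, so bias here means bias against that stated aim.
- The count, imbalance and effect of dilations are all assumed. This is correct, and the figures in the working should not be read as estimates.

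**Conclusion.** The concern holds and should be fixed. As written, the primary rule does not remove SDI scores obtained after a dilation, although the SAP calls dilation rescue and its responder rule treats it so. The inconsistency follows from the text alone and rests on no assumption.

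The numerical effect cannot be determined from the SAP. It is nil if no patient is dilated before week 10 or if use and effect are balanced. Under the assumed 3-point effect, each dilated patient in one arm only moves the treatment difference by 0.17 points at 18 per arm (3/18) or 0.14 at 22 per arm (3/22), with the direction set by the arm. In arms this small, a few patients are enough to matter.

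**What to change.** Before database lock and while still blinded, replace *rescue medication* with *rescue medication or procedure (including esophageal dilation)* in:
- the continuous bullet of 5.7.1;
- the primary MI step of 5.7.2;
- sensitivity analyses 2 and 3.

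Define the rescue date as the earlier of the first adjudicated rescue medication and the first recorded rescue procedure. Leave sensitivity analyses 1 and 4 as all-observed-data analyses. For consistency, match the introductory sentence of 5.7.1 and state how rescue procedures are identified, since 4.3 and Appendix 10.6 describe this for medications only.

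The cost is SAP wording and a small programming change. Rescue procedures must already be identified for the secondary rescue endpoint, so no new data are needed, and patient care is unaffected. The drawback is that a few more values may be set to missing and imputed, so the fix removes the distortion only as far as the imputation model holds for those values.

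### As written, the continuous-endpoint rescue rule covers medication but not procedures, so values after an esophageal dilation stay in the primary analysis while the same patient counts as a non-responder

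*SAP*

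**What the plan says.** Section 5.7.1 gives two rescue rules in adjacent bullets. The first reads "Continuous efficacy endpoints: if a patient receives rescue medication, the data collected after rescue medication initiated will be treated as missing". The second reads "Categorical efficacy endpoints: responder data will be counted as non-responders after use of rescue medication or procedure".

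The narrower trigger recurs wherever continuous data are handled. In the primary analysis (5.7.2), patients' "efficacy data through week 12 after rescue medication usage will be set to missing first" and are then imputed. Sensitivity analyses 2 (LOCF) and 3 (WOCF) both state: "The efficacy data will be set to missing after rescue medication is used". Section 5.7.3 sends the continuous secondary endpoints, EREFS among them, through the same approach as the primary.

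The wider trigger recurs for responder data in 5.7.3: "Patients with early withdrawals or use of rescue medication or procedure will be counted as non-responders".

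Elsewhere the SAP treats dilation as a form of rescue separate from medication. Section 2.3 says that "rescue medications or emergency esophageal dilation may be provided to study patients". Section 4.3 lists it among prohibited procedures, with the label "Esophageal dilation (considered rescue procedure". One secondary endpoint in 4.4.2 counts rescue by medication or procedure and gives dilation as the example. Rescue of either kind ends study drug (4.3) but not follow-up (2.3): "These patients will remain blinded and will be asked to return to the clinic for all remaining study treatment visits".

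**The concern.** One event, a dilation before week 10, is treated in two ways. It makes the patient a failure on the SDI responder endpoint. Under the wording of the continuous rule it has no effect on the primary endpoint, so the SDI score recorded afterwards enters the FAS analysis as if no rescue had occurred. Imputation for continuous data and failure for responder data can reasonably coexist, but nothing in the SAP explains why the two should act on different rescue events.

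The handling of a dilated patient in the primary analysis would then depend on how the programmer reads the phrase rescue medication. The planned sensitivity analyses would not reveal the difference. Analyses 2 and 3 share the wording, and analyses 1 and 4 keep all observed data by design. For a patient whose only rescue is a dilation, the primary analysis and sensitivity analysis 1 use the same values.

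**Working it through.** **The plan's own figures.** With 18 per arm, a difference of 3, SD 2.46 and a two-sided 5% t-test, the noncentral t distribution gives 94.4% power (SAP 2.2 states 94%). Allowing for 15% dropout, 18 / 0.85 = 21.2, rounded up to 22 per arm, as stated. Neither figure depends on the rescue rule.

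**The rules side by side.**

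| Place in SAP | Data | Trigger as written | Handling |
|---|---|---|---|
| 5.7.1, first bullet | Continuous | Medication | Missing |
| 5.7.2, primary | SDI change | Medication | Missing, then MI |
| 5.7.2, sensitivity 2 and 3 | SDI change | Medication | Missing, then LOCF or WOCF |
| 5.7.2, sensitivity 1 and 4 | SDI change | None (all observed data) | Kept |
| 5.7.1, second bullet | Responder | Medication or procedure | Non-responder |
| 5.7.3 | Responder | Medication or procedure | Non-responder |

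As written, no planned FAS analysis of a continuous endpoint sets post-dilation values to missing.

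**What the per-protocol set covers.** Appendix 10.1 lists the primary analysis on the PPS as supportive. Section 3.2 removes patients with under 80% of scheduled doses, and rescue by procedure stops dosing.

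- Scheduled doses: day 1 plus weeks 1 to 11 = 12 (5.5 counts the loading dose once).
- Threshold: 0.80 × 12 = 9.6, so 10 doses are needed.
- Dilation before the week-9 dose: at most 9/12 = 75%, excluded.
- Dilation after the week-9 dose, none missed: at least 10/12 = 83%, retained.
- Interval before the week-10 SDI that stays uncovered: day 64 to day 71, about 7 days (nominal days; visits carry ±3 days).

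Appendix 10.1 gives no supportive analysis for secondary continuous variables, so this cover does not extend to them.

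**EREFS.** Its stricture item scores estimated diameter from 0 to 4 (4.4.2), and a dilation acts directly on that diameter. Section 4.3 asks for efficacy assessments just before rescue, at an unscheduled visit if needed, and the endoscopy window in 6.4 maps unscheduled examinations on days 2 to 99 to week 12. Section 6.4 also ranks a scheduled record above an unscheduled one. The post-dilation score is therefore used when the patient later has the scheduled week-12 endoscopy, or when the only available examination falls after the dilation. If the pre-rescue endoscopy is the only one, it does not arise.

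**Scale.** The SAP gives no dilation rate and no effect of dilation on SDI. Let d be a dilated patient's retained week-10 change minus the average value MI would have supplied. With 22 per arm, the arm mean moves by about d/22 per such patient. Assume d is 1 to 3 points in size, in either direction:

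- 1/22 = 0.045, and 0.045/3 = 1.5% of the planned 3-point difference.
- 3/22 = 0.136, and 0.136/3 = 4.5%.

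With no dilations the shift is 0.

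**The case against.** The strongest reply is that this is loose wording and the rule was never meant to differ. One lead-in in 5.7.1 speaks of accounting for rescue medication and governs both bullets, yet the second bullet goes on to include procedures. Appendix 10.1 labels sensitivity analysis 1 as regardless of rescue, while 5.7.2 describes the same analysis in terms of rescue medication. The SAP does use the two terms interchangeably there. This stands as a plausible reading. It does not settle the matter, because the SAP never defines the shorthand and names procedures separately in 2.3, 4.3, 4.4.2 and 5.7.3.

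A reader might take the drugs-only search in 4.3 and Appendix 10.6 as proof that dilation was deliberately left out of the continuous rule. It is not. A proton pump inhibitor or glucocorticoid in the medication records may or may not be EoE rescue and has to be adjudicated, whereas 4.3 already classifies dilation. A medication list that contains only medications says little about how post-dilation data are handled.

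A reader might also infer that the bias is harmless because dilation would mainly improve placebo scores and so pull toward no effect. The SAP does not support a direction. The SDI has a 1-week recall, and its top intensity grade is an obstruction needing endoscopic intervention (4.4.1). A dilation within the recall week could produce a worse score than imputation would, and days 64 to 71, which the PPS leaves uncovered, are about that recall week for the week-10 score.

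It is also fair that the PPS narrows the exposure of the primary endpoint considerably. The PPS is supportive only, however, and the FAS is the primary population.

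**Conclusion.** The inconsistency is real on the text. Continuous data become missing only after rescue medication, responder data fail after rescue medication or procedure, and dilation is classed as a procedure. Followed literally, post-dilation SDI values stay in the primary FAS analysis. EREFS values do so only when a post-dilation week-12 endoscopy is the record used, so it would be wrong to say that EREFS is exposed whenever a dilation occurs.

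The size is unknown and may be nil. The figure of 0.05 to 0.14 points per dilated patient (1.5% to 4.5% of the planned difference) rests on an assumed 1 to 3 point discrepancy and on 22 per arm, and its sign is open. Nothing here changes the stated power or sample size, and the documents do not support a claim that the primary result is biased in a given direction. The point is worth correcting because it leaves a choice in the primary analysis to interpretation and can be closed with a few words before database lock.

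**What to change.** Write *rescue medication or procedure (including esophageal dilation)* in the continuous rule of 5.7.1, in the primary MI rule of 5.7.2, and in sensitivity analyses 2 and 3. Sensitivity analyses 1 and 4 use all observed data and need no change. In the blinded pre-lock review described in 4.3, flag recorded dilations as rescue events, with dates, so that the cut-off for each patient's data is fixed before unblinding.

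The cost is a short text change and a check of procedure records that are already collected, in about 44 planned patients. The downside is slightly more imputed data. Continuous and responder endpoints will still handle rescue differently (imputation against failure), but they will act on the same events.
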